8.3.3.2 Consent

To be accepted by the NHS talking therapies service participants need to consent to sharing of necessary data with their GP, as well as to data being stored safely and confidentially under GDPR regulations. Participants also need to consent to anonymised data being provided to NHSE, but can opt out of this if preferred.

Once the user downloads the app they are provided with information about how their data will be used together with an option to opt out. It will be made clear that patients have a right to withdraw from the study at any time and have their data removed. Declining consent will not affect patients' participation in the study or their clinical care.

8.3.4 Adherence

The study team will ensure that all Wysa cCBT programmes are used as intended, with the support of a qualified Psychological Wellbeing Practitioner.

8.4 Data Collection

8.4.1 Methods of Data Collection

The quantitative outcome measures will be taken during the e-triage (or for those who do not complete the Wysa electronic triage, when they onboard the App), and then every two weeks whilst engaged with the app. Participants who are in part 2 of the study will complete standard NHS

Version number 1.1 - 25th November 2023

talking therapies measures on a weekly basis.

Outcome measures have been chosen that will not be a significant burden for participants to complete; none of the questionnaires are longer than 9 items or expected to take more than a few minutes each to complete. Patient responses during e-triage and cCBT treatment will be automatically transferred to the NHS talking therapiesUS electronic patient record system. App use analytics will be stored by Wysa as data controller.

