From here the patient will be offered the opportunity to download the Wysa app as a waitlist support tool until they are offered an intervention. The Wysa app includes over 150 self care tools, conversational AI and daily check-ins and reminders via push notifications. We will analyse data collected from within the app to understand app usage and any effect use of the app may have on mental wellbeing markers during the wait period.

Patients who are then offered Wysa's cCBT by their assessing clinician will have access to diagnosis specific weekly web or app based programmes including psychoeducational videos and CBT conversational techniques, as well as periodic reviews by an NHS talking therapies clinician through a communication dashboard called the Therapist Companion, which is also fully integrated into the service EPR system. We will report on changes in clinical outcome measures and engagement metrics to understand the efficacy of these cCBT programmes.

For all patients using Wysa within the service there is a built in SOS response. Wysa has three pathways to crisis alert and response:

- Patients are able to trigger crisis help by selecting the 'SOS' button on the app.

Version number 1.1 - 25th November 2023

- Crisis response will be triggered by responses to PHQ9 question 9
- Crisis response will be triggered when risk language is used (and confirmed by the chatbot) within free text.

When Wysa or the user triggers the crisis response pathway, users will be offered to complete a safety plan, engage in grounding exercises, and be provided with local or national crisis helplines. We will collect data including the number of times that the Wysa SOS response is triggered, the number of false positives identified by the AI, and SOS tool usage.

After patients have been discharged, Wysa can also be used as a support/ relapse prevention tool. All participants will have access to the AI Chatbot and self tools for 12 months from onboarding.

[figure not shown]

Figure 1. Current NHS talking therapies care pathway flows including Wysa therapeutics.

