8.2.3 Interventions

Wysa therapeutics include;

- An electronic triage, comprising of two parts:
 - a referral triage, comprising demographic information and some limited questions around physical health and past contact with mental health services
 - a clinical assessment triage, comprising a wide range of clinical questions and standardised outcome measures.
- Waitlist support;
 - 24/7 conversational care,
 - Access to over 150 self care tools
 - Daily check-ins to increase engagement and promote behavioural change.
- A range of diagnosis specific, NICE compliant therapist enabled step 2 cCBT programmes, delivered to patients via an app or widget. Each programme consists of 6-8 weekly modules, with each module focussing on a specific CBT principle or intervention. Psychoeducation is provided through short videos, with CBT techniques introduced in each video practised through conversational AI and augmented with self care audios and editable worksheets. The programmes also include the collection of standardised NHS talking therapies clinical outcome measures.

Wysa is delivered as a standalone system which patients download directly onto their personal device. Upon e-triage self-referral or alternative route referral to NHS talking therapies services the individual is automatically sent a download link via sms, email or QR code. Once downloaded, data from within the app, including outcome measures, tools used and crisis alerts are automatically pushed to the electronic patient record (iaptus) using the Mayden Prism software.

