8.2.4 Outcomes

8.2.4.1 Primary Outcomes

In order to understand the impact of Wysa therapeutics across the care pathway we will be conducting two distinct analyses. In Part 1 we will be focusing on e-triage and in Part 2 we will be focussing on the waitlist support and cCBT programmes.

The primary analysis in Part 1 will be a comparison of the time spent by the clinician to make a decision on the treatment pathway for those who complete the Wysa e-triage, with that taken to make a decision for patients who do not. The primary outcome measure will be time taken for the clinician to make a decision, for each of these two assessment pathways.

The primary analysis in Part 2 will be a comparison of depression and anxiety scores before and after a Wysa intervention (waitlist self care or step 2 cCBT). The primary outcomes will be measured at onboarding, start of intervention and discharge from intervention. In line with the national recommendations laid out by the NHS talking therapies Manual, we will be using Wysa's AI automation to encourage users to complete the Patient Health Questionnaire (PHQ-9 [15) and General Anxiety Disorder (GAD-7 [16]) routine outcome measures.

	Primary Outcome	Outcome Measure
Part 1: E-triage	Clinical Time Savings	Hours/Minutes
Part 2: Waitlist and cCBT	Depression or Anxiety severity	Score on the PHQ9 and GAD7

Table 5. Primary Outcome Measurement

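### Protocol sections 8.2.4.1 and 8.4.1 disagree on the first primary-outcome score, leaving the waitlist self-care baseline dependent on triage route

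*Protocol*

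**What the plan says.** Protocol section 8.2.4.1 defines the Part 2 primary analysis as a "comparison of depression and anxiety scores before and after a Wysa intervention (waitlist self care or step 2 cCBT"). On timing it says: "The primary outcomes will be measured at onboarding, start of intervention and discharge from intervention". It lists no e-triage time point and makes no distinction by route.

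Section 8.4.1 sets a different first time point. The measures are "taken during the e-triage (or for those who do not complete the Wysa electronic triage, when they onboard the App"). App users repeat them at two-week intervals for as long as they remain active. Part 2 participants also complete the standard "talking therapies measures on a weekly basis"; no start point for the weekly series is given.

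On the order of events, section 8.2.3 describes the second part of the e-triage as "a clinical assessment triage, comprising a wide range of clinical questions and standardised outcome measures". It then says: "Upon e-triage self-referral or alternative route referral to NHS talking therapies services the individual is automatically sent a download link". Section 6, after describing the triage, continues: "From here the patient will be offered the opportunity to download the Wysa app as a waitlist support tool".

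Section 8.3.2.1 states that the study has no control arm.

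**The concern.** A before-after change can be read as change during exposure only if the 'before' score is taken when exposure starts. Under section 8.4.1 that holds for patients who enter by another route, because they are first measured when they onboard the app. It need not hold for e-triage completers, who are first measured at a step that precedes the download.

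The comparison at stake is waitlist self care, one of the two named in the Part 2 primary analysis and the subject of study aim 2 in section 5. Section 8.5 foresees comparing users with non-users, but the Part 2 primary analysis is within-patient. Nothing in it separates change before the app from change during its use. Because the difference follows triage route, and e-triage is itself under evaluation, any artefact would also be mixed up with one of the study's own components.

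**Working it through.** The protocol gives no figure to reproduce here: no lag, no expected drift and no share of patients using e-triage. The check is therefore a comparison of time points, followed by an illustration on stated assumptions.

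**Step 1: time points by route**

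| | E-triage completers | All others |
|---|---|---|
| First score, section 8.4.1 | during e-triage | app onboarding |
| First score, section 8.2.4.1 | onboarding | onboarding |
| App download (sections 6 and 8.2.3) | after e-triage | after referral by another route |
| Score scheduled at app onboarding by 8.4.1 | none | yes |
| Score at start of intervention (8.2.4.1) | yes | yes |

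After e-triage, the next in-app score for completers belongs to the two-weekly series. Section 8.4.1 does not tie that series to onboarding, so it does not guarantee a score at the start of app use.

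**Step 2: what the change contains**

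Write change as earlier score minus later score, so that improvement is positive.

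- Completers: (e-triage − end of wait) = (e-triage − app onboarding) + (app onboarding − end of wait)
- Others: (app onboarding − end of wait)

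The first bracket for completers is change before app use. It has no counterpart in the other route.

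**Step 3: illustrative size**

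All three inputs are assumptions: a lag L of 0 to 4 weeks from e-triage to onboarding, a drift d of 0.25 to 0.5 PHQ-9 points of improvement per week without the app, and a share p of 0.5 using e-triage.

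- Shift in completers = L × d. Minimum: 0 × d = 0. At 4 weeks: 4 × 0.25 = 1.0 to 4 × 0.5 = 2.0 points.
- Shift in the pooled mean = p × L × d. Minimum: 0. At 4 weeks: 0.5 × 1.0 = 0.5 to 0.5 × 2.0 = 1.0 point.
- If patients worsen at the same rates while waiting, d is negative and the ranges become −2.0 to 0 in completers and −1.0 to 0 pooled.

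**Step 4: cCBT**

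If the start-of-intervention score is 'before' for cCBT, both routes share that baseline and the shift is nil.

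**The case against.** The strongest reply is that no section calls the e-triage score the 'before' score. Section 8.2.4.1, which governs the primary analysis, names onboarding, and choosing a baseline among scheduled scores is commonly left to a statistical analysis plan. This stands in part: what the text shows is two unreconciled schedules, not a declared e-triage baseline. But a later plan can only choose among scores that were collected, and section 8.4.1 schedules none at app onboarding for completers.

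A second reply is that onboarding is undefined. Section 8.1.1 uses the word for study entry, so section 8.4.1 may simply spell out entry by route. On that reading the contradiction disappears, but the route-dependent baseline is then what the protocol intends.

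Third, the lag may be negligible. The link is sent automatically, and section 7.2 presents the app as support available at once on referral. This stands: zero belongs in the range. Still, an automatic link fixes when it is sent, not when the patient installs the app, and the protocol does not say that the interval will be recorded.

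A reader might infer that the waitlist benefit is overstated, since people are measured as they seek help and regression to the mean would then favour the app. That is plausible, but the documents do not establish it. Section 7.1 describes long waits as harmful, with 38% of those waiting contacting crisis services, and deterioration would push the other way. A reader might also extend the problem to the whole of Part 2. The start-of-intervention score, available whatever the route, does not support that.

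**Conclusion.** The point holds, limited to waitlist self care. Sections 8.2.4.1 and 8.4.1 need reconciling on the first primary-outcome score. Followed as written, section 8.4.1 gives e-triage completers a first score that precedes app download and no scheduled score at app onboarding. With a purely before-after comparison, any change in that interval is counted as change on the app, in one route only.

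Direction and size are unknown from the documents. The illustrative 0 to 2.0 PHQ-9 points in completers, and 0 to 1.0 pooled, rest entirely on the assumed lag, drift and share. The shift vanishes if onboarding follows e-triage on the same day, and it changes sign if patients worsen while waiting.

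This is also an addition to a larger limitation that it does not explain: natural recovery and regression to the mean during app use remain in both routes under any baseline. It is worth correcting now because a missing onboarding score cannot be recovered at analysis.

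**What to change.** Reconcile the two sections as follows.

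- In section 8.4.1, have every app user, including those who completed e-triage, complete PHQ-9 and GAD-7 at app onboarding.
- In section 8.2.4.1, state that onboarding means app onboarding. Name that score as 'before' for waitlist self care and the start-of-intervention score as 'before' for cCBT.
- Keep the e-triage score as descriptive information, and record days from referral to app onboarding so that the interval can be reported by route.

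The cost is one additional in-app questionnaire set for e-triage completers, which section 8.4.1 itself expects to take no more than a few minutes per questionnaire, plus a sentence or two in each section. The change gives both routes a common baseline at the start of exposure. It does not supply a control for change during app use.

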8.1.1 Timeline

The study will last for 10 months: 3 months of evaluation, refinement and technical integration, 6 months of data collection (the total time period for each participant journey will be approximately 20 weeks, thus allowing a 4 week onboarding window), and 1 month of post-evaluation analysis and preparation for dissemination.

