8.5 Data Analysis

Descriptive and comparative statistics will be used to evaluate outcomes for those who use Wysa and those who do not, as well as clinical recovery, calculated by reduction in scores on the Standard NHS talking therapies measures as per NHS talking therapies guidelines [4]

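### Part 2 ties its primary comparison to onboarding, start and discharge scores and gives the interim PHQ-9 and GAD-7 scores no role in it, although they would help where discharge scores are missing

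*Protocol*

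**What the plan says.** Protocol Section 8.2.4.1 fixes both the form and the timing of the Part 2 primary comparison: "The primary analysis in Part 2 will be a comparison of depression and anxiety scores before and after a Wysa intervention", and "The primary outcomes will be measured at onboarding, start of intervention and discharge from intervention".

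Section 8.4.1 collects far more. The measures are taken at entry "and then every two weeks whilst engaged with the app. Participants who are in part 2 of the study will complete standard NHS" and, continuing over the page, "talking therapies measures on a weekly basis". Section 8.2.3 gives the length of the cCBT phase: "Each programme consists of 6-8 weekly modules, with each module focussing on a specific CBT principle or intervention". Section 8.1.1 says that "the total time period for each participant journey will be approximately 20 weeks, thus allowing a 4 week onboarding window".

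Section 8.5 names no model. It offers descriptive and comparative statistics and "clinical recovery, calculated by reduction in scores on the Standard NHS talking therapies measures", following the national guidelines.

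Three other places matter. Section 8.2.4.2 (Table 6) lists dropout and non-attendance as outcomes, so losses are expected. Section 8.2.1 says that only a subset of patients accepted for step 2 treatment will use cCBT. Section 9.1 says that all participants will enter the quantitative analyses.

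**The concern.** A weekly schedule over 6-8 modules yields about 7-9 scores per cCBT participant, counting the start score. The primary comparison names two of them for that phase. The rest have no stated place in it.

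This matters most for participants who stop early. A paired before-after difference needs both scores. Someone without a discharge score drops out of it unless a value is substituted, and the protocol gives no rule for that. The two-weekly scores depend on continued app use, so participants who disengage are the ones likely to lack the later scores. Two things are at stake: precision in a study with a minimum of 100 patients (Section 8.3.2.1), and a result that may describe those who stayed and not those who started.

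**Working it through.** **Inputs from the protocol.** Weekly scores over 6-8 modules give 7 or 9 scores at the two ends of the range. The minimum sample is 100. The protocol gives no SD, correlation, dropout rate, alpha or power, so there is no plan figure to reproduce, and everything below is in SD units with assumed values.

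**1. Complete data, a separate mean at each visit.** With equal SD at each visit and start-discharge correlation ρ, the variance of the mean change is 2(1-ρ)/n. For ρ = 0.5 and n = 100 this is 0.01, so the SE is 0.100 SD. Generalised least squares on all seven or nine scores, with a free mean at each visit, gives the same value. The SE ratio is 1.00 under compound symmetry, AR(1) and a mixed structure (correlation 0.4 + 0.6 × 0.8^lag). The interim scores add nothing here.

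**2. Discharge scores missing.** Nine visits. A fraction d of participants stops early, spread evenly over the weeks, and everyone has a start score. Start-discharge correlation is 0.5 (0.50 in the mixed structure). Visit means are free, so no trend is imposed.

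- Completers only: SE = √[2(1-ρ)/(n(1-d))]. At d = 0.4 this is √(1/60) = 0.129.
- Likelihood analysis of start and discharge only: SE = √{[(1-ρ²)/(1-d) + ρ² + 1 - 2ρ]/n}. At d = 0.4 this is √[(0.75/0.6 + 0.25)/100] = √0.015 = 0.122.
- All visits: invert the information summed over the dropout patterns. At d = 0.4 the SE is 0.118 (compound symmetry), 0.116 (mixed) and 0.114 (AR(1)).

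| Discharge missing | SE, completers | SE, two-point likelihood | SE, all visits | All visits / completers | All visits / two-point |
|---|---|---|---|---|---|
| 20% | 0.112 | 0.109 | 0.106-0.107 | 0.95-0.96 | 0.97-0.99 |
| 40% | 0.129 | 0.122 | 0.114-0.118 | 0.88-0.92 | 0.93-0.97 |
| 50% | 0.141 | 0.132 | 0.119-0.126 | 0.85-0.89 | 0.90-0.96 |

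Against completers, the unrounded ratios (0.947-0.960, 0.883-0.916, 0.845-0.893) mean SEs smaller by 4-5%, 8-12% and 11-16%. Part of that comes simply from keeping the start scores of those who leave. The last column shows what the interim scores themselves add.

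**3. Complete data with a straight line imposed.** Write s_e for the weekly error SD and s_d for the SD of true change. The per-patient variance of last minus first is 2s_e² + s_d². From all weekly scores it is s_e²·T²/Σ(t - t̄)² + s_d², with T²/Σ = 36/28 for T = 6 and 64/60 for T = 8. Assume s_e = 2 to 3.5 and s_d = 3 to 4 points.

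- Smallest gain (T = 6, s_e = 2, s_d = 4): 24.0 against 21.1. The SE ratio is 0.94, worth 14% more patients.
- Largest gain (T = 8, s_e = 3.5, s_d = 3): 33.5 against 22.1. The SE ratio is 0.81, worth 52% more patients.

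This needs independent weekly errors. With AR(1) error in the same model, the SE ratios over both lengths are 0.88-0.96 at weekly correlation 0.2, 0.94-0.98 at 0.4 and 0.98-1.00 at 0.6. The line also has a price if improvement flattens. For a log(1+t) course, the fitted slope times T recovers 94% of the true change at 6 weeks and 91% at 8 weeks.

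**The case against.** The strongest reply is that this belongs to the statistical analysis plan. Section 8.5 names no model, and a repeated-measures model could estimate the before-after contrast that Section 8.2.4.1 defines. This stands in part: a reader might infer that the interim scores are discarded, and the protocol does not say so. They also have other uses. Section 6 plans to analyse in-app data from the waiting period, and links PHQ-9 question 9 to the crisis response. But the protocol itself fixes the time points and form of the primary comparison, and gives the interim scores no place there.

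A reader might also infer that the plan is needlessly imprecise as it stands, by 14% to 52% of the sample. The documents do not support that. The figure needs complete data, a linear trend and independent weekly errors, and the protocol states none of these. It falls to about zero under strong serial correlation, and to exactly zero with complete data and free visit means. Imposing a line could also bias the estimate.

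The recovery measure cannot be judged either way, because Section 8.5 defines it through an external guideline. The Section 9.1 statement is offered as protection against recruitment bias, so it is not a missing-data rule. It still does not fit a comparison that omits anyone lacking a discharge score.

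**Conclusion.** The point holds in a limited form. The primary comparison rests on three time points, the interim scores have no stated role in it, and a plain before-after analysis would leave out participants without a discharge score, contrary to Section 9.1. The benefit of using all scheduled scores lies in handling those missing scores: an SE about 4-16% smaller than a completer analysis with 20-50% of discharge scores missing, and less completer bias. With complete data there is no gain unless a trend shape is assumed.

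The size rests on assumed dropout rates and correlations, on dropout spread evenly over the weeks, and on a discharge score that falls at the last weekly visit. It covers the cCBT phase only. The waitlist phase was not computed, because its length is not stated. The grade is minor: a cheap improvement, not an error that undermines the study.

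**What to change.** In Sections 8.2.4.1 and 8.5, keep the onboarding-to-start and start-to-discharge changes in PHQ-9 and GAD-7 as the targets. State that they are estimated with a likelihood-based repeated-measures mixed model on all scheduled scores, with time as categorical visits so that no trend shape is imposed. Say which scheduled score counts as start and which as discharge. Report the simple paired change as a sensitivity analysis, and optionally a linear-trend model as another. Say that participants without a discharge score contribute the scores they have, which brings the analysis into line with Section 9.1.

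The cost is wording and slightly more analysis work; no new data, visits or patients are needed. The model relies on scores being missing at random given those observed. This is weaker than what a completer analysis needs, but it is still an assumption and should be stated.

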8.5 Data Analysis

Descriptive and comparative statistics will be used to evaluate outcomes for those who use Wysa and those who do not, as well as clinical recovery, calculated by reduction in scores on the Standard NHS talking therapies measures as per NHS talking therapies guidelines [4]

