6 STUDY FLOW CHART

Wysa is delivered as a standalone system that patients download directly onto their personal device. Wysa will be made available to patients as a self referral and clinical triage tool, and further along the care pathway will provide a range of therapist enabled computerised CBT programmes.

This study will conduct a quantitative feasibility review of Wysa as an AI therapeutic support tool across a typical care pathway in adult NHS talking therapies services. The study will take place in a collaborating NHS service utilising Wysa as an offer for all patients who have a suitable digital device.

Wysa's suite of products can be utilised at four key points in the care pathway:

- 1. Referral
- 2. Waitlist
- 3. NHS talking therapies step 2 intervention
- 4. Post discharge

The study will compare data from patients who use Wysa throughout their NHS talking therapies journey, or for at least a part of their journey, with those who do not.

Following self-referral (either using the Wysa electronic triage tool or another method such as self referral portal or email) or professional referral, the individual is provided access to the Wysa app via a download link. The patient can then use the app for support whilst waiting for their next contact with the service. Where the clinician has identified that a Wysa cCBT programme is an appropriate treatment intervention, this will be prescribed via an additional download link.

Wysa's Triage tool collects demographic and clinical patient related information via the AI chatbot. This tool will support patients to complete a referral to NHS talking therapies services, allowing the service to collect the data (via an API to their EPR system) required for a referral to be opened and a clinician to make a decision about the patient's care. Here we will review predetermined data points to understand how patients engage with the e-triage and the types of patients who utilise the tool. We will also compare the time taken for the clinician to reach a clinical outcome decision when the Wysa e-triage is completed with the time taken when a standard assessment is undertaken.

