8.2 Study Context

8.2.1 Participants

The target population of the study will include patients who are 16+ who are referred, or self-refer to NHS talking therapies adult mental health services for support, and who at any stage of their NHS talking therapies journey, download and use any of the Wysa functionality.

The cCBT programmes will be accessed by a subset of the patients who are accepted for step 2 treatment. Step 2 treatment is usually offered to patients experiencing mild or moderate depression and/ or anxiety symptoms as recommended by NICE guidelines for stepped care in NHS talking therapies services.

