8.3.2 Sampling

8.3.2.1 Sample Size

All patients accepted by the NHS talking therapies services and meeting the inclusion criteria will be eligible for the study. A minimum of 100 patients will be recruited in order for the study to be able to conclude statistical validity. This is primarily a quantitative feasibility review with no control arm.

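### The planned user versus non-user comparison of clinical scores has no comparator group or score collection behind it, and the protocol contradicts itself about whether non-users are in the study

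*Protocol*

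**What the plan says.** Section 8.5 is the protocol's general analysis statement: "Descriptive and comparative statistics will be used to evaluate outcomes for those who use Wysa and those who do not", together with clinical recovery derived from score reductions. Section 6 describes the same contrast as "patients who use Wysa throughout their NHS talking therapies journey, or for at least a part of their journey, with those who do not".

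Other sections bear on whether that contrast can be made:

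- Section 8.3.2.1: "This is primarily a quantitative feasibility review with no control arm".
- Section 8.2.1: the target population is referred patients who, at any stage, "download and use any of the Wysa functionality".
- Section 8.3.3.1, Part 2: participants must agree to a Wysa cCBT programme. Section 8.3.2.2 requires consent to digital treatment.
- Section 8.4.1: measures are taken during e-triage ("or for those who do not complete the Wysa electronic triage, when they onboard the App"), then fortnightly while the patient is engaged with the app, and weekly for Part 2 participants.
- Section 8.2.4.1: the Part 2 primary analysis compares scores before and after a Wysa intervention. The Part 1 primary analysis compares clinician decision time between patients who complete the e-triage and those who do not.
- Sections 8.3.1.1, 8.3.2.1, 8.3.2.2 (Part 1) and 8.3.3.1 (Part 1): eligibility covers accepted patients who meet the criteria, with no requirement to use Wysa.

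**The concern.** The primary objective in section 7.4 asks whether Wysa therapeutics improve clinical outcomes. The designated Part 2 analysis is before-after within users, so it describes change but has no comparator against which to attribute it. The user versus non-user contrast is the only between-group evidence on clinical scores that the protocol mentions, and section 10.1 intends the data to support a regulatory submission. If the comparator group does not exist, the promised result cannot be delivered. If one is assembled afterwards, its make-up will depend on who chose, or was chosen, to use Wysa.

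This cannot be left to a statistical analysis plan. Such a plan can choose a model, but it cannot supply a group that the population definition excludes and whose scores the protocol does not arrange to collect.

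**Working it through.** **1. Is there a non-user group for clinical scores?**

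| Question | Text implying non-users | Text excluding or omitting them |
|---|---|---|
| Is the comparison planned? | Sections 6 and 8.5: yes | Section 8.3.2.1: no control arm |
| Who is in the population? | Sections 8.3.1.1, 8.3.2.1, 8.3.2.2 (Part 1), 8.3.3.1 (Part 1): accepted patients, Wysa use not required | Section 8.2.1: users of some Wysa function; section 8.3.3.1 (Part 2): those agreeing to Wysa cCBT |
| When are scores taken? | None stated | Section 8.4.1: e-triage, app onboarding, fortnightly during app use, weekly in Part 2 |

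Every score time point in section 8.4.1 is tied to Wysa use or to Part 2 membership, and Part 2 membership requires agreement to Wysa cCBT. A patient who never uses Wysa therefore has no specified baseline or follow-up score. Section 8.2.4.1 calls PHQ-9 and GAD-7 routine measures, so service records may hold them. The protocol does not name those records as the source for a comparison group, define such a group or set its time points.

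**2. If non-users were found, how is exposure defined?** Section 6 counts as a user anyone using Wysa throughout the journey "or for at least a part of their journey, with those who do not". Status is thus fixed by behaviour after entry, and a longer time in the pathway gives more opportunity to become a user. For cCBT, section 6 adds selection by the clinician. Device ownership and willingness also differ between users and non-users. No allocation process balances any of this.

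**3. The sample size.** Section 8.3.2.1 says: "A minimum of 100 patients will be recruited in order for the study to be able to conclude statistical validity". The figure of 100 cannot be reproduced, because no effect size, SD, power, alpha or user/non-user split is given. Purely for illustration, I assume two-sided alpha 0.05 and 80% power. The detectable difference in SD units is (1.960 + 0.842) × √(1/n_users + 1/n_non-users):

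| Users : non-users | √(1/n + 1/n) | Detectable difference |
|---|---|---|
| 50 : 50 | 0.200 | 0.56 SD |
| 70 : 30 | 0.218 | 0.61 SD |
| 80 : 20 | 0.250 | 0.70 SD |
| 90 : 10 | 0.333 | 0.93 SD |
| 100 : 0 | undefined | no estimate |

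**4. What selection alone could do.** Assume no true effect, a 50 : 50 split (standard error 0.200 SD) and a pure selection difference of b SD. The two-sided 5% test then rejects with probability 1 − Φ(1.960 − b/0.2) + Φ(−1.960 − b/0.2):

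| Assumed b | Rejection rate |
|---|---|
| 0 | 5.0% |
| 0.1 | 7.9% |
| 0.2 | 17.0% |
| 0.3 | 32.3% |
| 0.5 | 70.5% |

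The values of b are assumptions. The protocol gives nothing from which to choose among them.

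**The case against.** **The protocol does not admit only Wysa users.** A reader might infer from section 8.2.1 that it does. That is too strong. The inclusion criteria and the Part 1 sampling and identification text require no Wysa use, and section 9.1 likewise speaks of everyone who meets eligibility and consents. The restriction is exact only for section 8.2.1 and for Part 2. This part of the objection stands, but it leaves the protocol with two incompatible populations rather than a working comparator.

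**Part 1 has a comparator.** The clinician-time analysis sets e-triage completers against non-completers, needs no PHQ-9 or GAD-7 baseline, and fits the wording of section 8.5. This stands. The defect is confined to clinical scores, and simply deleting the statements in sections 6 and 8.5 would remove text that supports a legitimate, though non-randomised, primary analysis.

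**The contrast is not the designated primary clinical analysis.** Section 8.2.4.1 gives that role to the before-after comparison. This also stands. It lowers the contrast's formal status but does not make it available.

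**The bias cannot be sized in PHQ-9 points.** A reader might try to do so by simulating waiting and uptake times. The documents do not support this. For example, assume no Wysa effect, gamma-distributed waits (shape 2, scale 4; mean 8 weeks), improvement of 0.25 points per week, and 56% of patients willing to start at a uniform time within 4 weeks. Users then appear 0.36 points better if change is counted from referral, but about 0.1 points worse if users' change is counted from onboarding. Even the direction rests on inputs the protocol does not give.

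**Conclusion.** The concern holds for clinical scores (PHQ-9, GAD-7, recovery) and should be fixed before analysis. Sections 6 and 8.5 plan a user versus non-user comparison, while sections 8.2.1, 8.3.2.1, 8.3.3.1 (Part 2) and 8.4.1 provide neither the group nor its scores. The protocol also contradicts itself about whether non-users are participants. This conclusion rests on the text alone.

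If non-users are found regardless, an unadjusted difference would be biased by self-selection, time-dependent exposure and clinician selection. The size is not determinable from the documents. The detectable differences and rejection rates above are illustrations under stated assumptions, not estimates for this study. The conclusion does not extend to the Part 1 clinician-time comparison.

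**What to change.** **Simplest option.** In sections 6 and 8.5, limit the clinical-score analysis to the before-after comparison of section 8.2.4.1, and draw no between-group conclusion on clinical outcomes. Align the population statements in sections 8.2.1, 8.3.2.2 and 8.3.3.1.

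**If a comparison is wanted.** It depends on the Trusts being able to supply routine electronic-record scores on a suitable legal basis. That basis has to be settled first: section 8.3.1.1 makes informed consent an inclusion criterion, and sections 9.7 and 9.11 do not say that the planned agreements cover non-participants. Then:

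- define a concurrent non-user group at the same sites, with the same eligibility and the same score time points;
- fix exposure at the start of follow-up, separately for waitlist support and for cCBT, since cCBT is prescribed later in the pathway;
- adjust for baseline score, age and site, and report the result as an association;
- reconcile sections 8.2.1, 8.3.2.1, 8.3.2.2, 8.3.3.1 and 8.4.1.

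**Under either option.** Keep the Part 1 clinician-time comparison as a separate analysis, labelled non-randomised.

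**A separate correction.** Sections 8.3.3.2 and 9.6 say that declining consent will not affect patients' "participation in the study or their clinical care". That conflicts with the consent criterion in section 8.3.1.1. The text should say that declining means no study participation and has no effect on care.

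**Cost.** A protocol amendment and a weaker claim. The second option adds a data extract and still leaves residual confounding.
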